- I The ABPM **device** is attached on the mornings of Visit 2.2, 5.1 and 7.1 before medication intake for measuring ABPM. This also applies to visits for repeat ABPM testing if required. Patients must have a successful completion of V2.2 ABPM prior to randomisation. Do NOT contact IRT system or dispense randomised study drug until after a successful 24-hour ABPM is complete. If after two attempts a successful reading is not achieved at either Visit 5.1 or Visit 7.1, patients should continue with the next scheduled visit (Visit 5.2/Day 85 or Visit 7.2/Day 169 respectively).
In case the ABPM must be repeated, the patient should continue taking trial medication. If possible, ABPM should take place within the visit window in the [Flowchart](#). If two doses of study medication are taken when the monitor is attached, then the ABPM should be repeated.

At the conclusion of each attempt, patient should be allowed to rest for at least 15 minutes after removal of the ABPM and a trough seated blood pressure measurement should be taken prior to intake of study medication.

- L Instruction and handover of device at Visit 2.1. Daily measurements during Run-in and Follow-up should be performed. During the treatment period, a weekly test is recommended. During the whole trial participation, additional measurements should be done in case of hypo- or hyperglycemia related symptoms.
- M At all visits the respective kit number has to be allocated to the patient via an interactive response technologies (IRT) system. All visit activities must be completed before contacting IRT.
- N At Visit 4 all patients will be dose escalated through an IRT system.
- O Visit 6 will be conducted as a phone visit.

- Q All visit activities must be completed and continued eligibility for randomisation or dosing confirmed prior to using IRT.
- R At Visit 2.1 the food log is dispensed only and to be completed for three consecutive days prior to Visit 3.

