5 ENDPOINT(S)

[figure not shown]
Note that several imputation methods will be used for the analysis of efficacy endpoints. Further details can be found in [Section 6.6](#).

Throughout the TSAP, the following should be considered:

- Successful is defined by the vendor BioClinica Inc. as a set of ambulatory blood pressure measurements (ABPM) readings meeting all of the following criteria:
 - Start time must be between 07:00 and 11:00
 - Minimum duration of 24 hours after beginning of the test
 - Minimum of 70% valid readings in the period
 - Total Required Hours is 18 (minimum valid readings for Required Hour is 1)
 - Total Exception Hours is 6 (minimum valid readings for Exception Hour is 0)
 - Total Consecutive Exception Hours is 2
- Valid is defined by the vendor BioClinica Inc. as a reading meeting all of the following criteria:
 - Systolic blood pressure (SBP) between 60 mmHg and 261 mmHg inclusive
 - Diastolic blood pressure (DBP) between 40 mmHg and 151 mmHg inclusive

- 
- Usable is defined as a reading within 24 hours of the beginning of test.
 - All ambulatory endpoints will be calculated by using successful, valid and usable ambulatory blood pressure (BP)/HR readings only. If any ambulatory BP/HR reading is not successful, valid or usable, then the corresponding ambulatory BP/HR measurements will also be set to not successful, valid or usable.
 - All 24-hour means are defined as the mean of hourly means (based on clocktime) of successful, valid and usable readings.
- 

- 
- Mean trough ambulatory BP is defined as the mean of successful, valid and usable readings measured from 22:00 until 23:59 hours after the beginning of the test.
 - Trough seated BP is defined as the mean of the seated/in office vital signs measurements including those taken after the removal of the ABPM device taken on the day of the clinic visit prior to trial drug intake.

- 
- PP is defined as (SBP - DBP).

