For ABPM data only the first available successful ABPM reading at each of the ABPM time points (Visit 2.2, 5.1 and 7.1) will be used and not the closest to the protocol planned day. Data from a repeated second reading after a successful one at the same ABPM time point will be ignored for the analysis as no second reading should be conducted after one successful first attempt according to protocol and eCRF description.

Note: For LOCF imputation, the last observed on-treatment value will be carried forward within the applicable period, whether or not it was selected in the previous time window. For interpolation only selected values are to be used. For more details on LOCF refer to [Section 6.6](#).

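### SAP 6.7 discards an ABPM repeat after a technically successful session because the protocol supposedly never calls for one, yet the protocol does so in two situations (minor)

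*SAP*

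**What the plan says.** SAP 6.7 states that "only the first available successful ABPM reading at each of the ABPM time points (Visit 2.2, 5.1 and 7.1) will be used", and not the session nearest the planned day. On later sessions it says: "Data from a repeated second reading after a successful one at the same ABPM time point will be ignored for the analysis". They are dropped "as no second reading should be conducted after one successful first attempt according to protocol and eCRF description". The SAP history table dates this clarification to the revision of 24 March 2017. SAP 4 says that the plan follows protocol amendment 4 of 18 July 2016, so the rule was written against the current protocol.

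SAP 5 defines a successful session by vendor criteria and applies the definition throughout the plan: start between 07:00 and 11:00, at least 24 hours' duration, "Minimum of 70% valid readings in the period", and limits on hours without a valid reading. Valid readings are defined by blood pressure limits. "Usable is defined as a reading within 24 hours of the beginning of test". The visible text has no condition on dosing and none on the session's mean SBP.

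The protocol gives two reasons for a repeat that are not technical failures:

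- Flow Chart footnote I: "If two doses of study medication are taken when the monitor is attached, then the ABPM should be repeated".
- Protocol 5.1.2 and 6.2.1 (Visit 2.2): the session is to be repeated if it fails quality control or if its mean SBP lies outside the required range, which inclusion criterion 5 sets at 135-175 mmHg.

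SAP 6.7 also defines baseline in general as the last measurement before randomised medication.

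**The concern.** A site that follows footnote I repeats a session in which two doses were taken. If the first session met the vendor criteria, SAP 6.7 analyses that session and ignores the repeat. The same happens at Visit 2.2 when the first session passes quality control with a mean SBP out of range. The repeat that made the patient eligible is then ignored, and the baseline comes from the session that did not qualify.

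Two confirmatory endpoints use these data: the week-12 changes in mean 24-hour ambulatory SBP (step II) and mean trough ambulatory SBP (step III). Each rests on one post-baseline session. The trough endpoint is the more exposed: "Mean trough ambulatory BP is defined as the mean of successful, valid and usable readings measured from 22:00 until 23:59 hours" after the start of the test. The first dose is given just after the start. A second dose on the monitor would therefore most plausibly be the next morning's tablet, taken before removal at 23:30-24 hours. Protocol 4.1.4 and 6.1 already anticipate tablets taken before a clinic visit. Any blood pressure response to that dose would occur in the empagliflozin arm only.

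**Working it through.** **1. The rules side by side**

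| Situation | Protocol | SAP 5: successful? | SAP 6.7 analyses |
|---|---|---|---|
| First session fails the vendor criteria | Repeat | No | The repeat; no conflict |
| Two doses on the monitor, vendor criteria met | Repeat (footnote I) | Yes, on the visible criteria | First session; repeat ignored |
| Visit 2.2, vendor criteria met, mean SBP out of range | Repeat (5.1.2, 6.2.1) | Yes, on the visible criteria | First session; repeat ignored |

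Rows two and three contradict the reason given in SAP 6.7. The list of important protocol violations in SAP 6.2 has no entry for two doses during a recording.

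**2. Visit 2.2.** Both doses there are run-in placebo, so only the out-of-range case matters. Taking the first session as baseline also departs from the general definition of baseline as the last measurement before randomised medication. The choice is made before randomisation, so it should not favour either arm. Its consequence is an analysed baseline that may lie outside 135-175 mmHg and differ from the session that determined eligibility.

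**3. Possible size at week 12.** The documents give no frequency of double dosing and no post-dose effect on SBP, so these are assumptions:

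- f, share of empagliflozin recordings with two doses that are kept: 1% to 10% (of 64 evaluable patients per arm, 0.6 to 6.4)
- e, extra SBP fall after the second dose: 1 to 5 mmHg
- h, post-dose hours inside the 2-hour trough window: 0.5 to 2

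Formulas: bias in the trough difference = f × e × h/2; bias in the 24-hour difference = f × e × h/24.

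| Case | Trough (mmHg) | 24-hour mean (mmHg) |
|---|---|---|
| Low: 1%, 1 mmHg, 0.5 h | 0.01 × 1 × 0.5/2 = 0.0025 | 0.01 × 1 × 0.5/24 = 0.0002 |
| Middle: 5%, 3 mmHg, 2 h | 0.05 × 3 × 2/2 = 0.15 | 0.05 × 3 × 2/24 = 0.0125 |
| High: 10%, 5 mmHg, 2 h | 0.10 × 5 × 2/2 = 0.50 | 0.10 × 5 × 2/24 = 0.042 |

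**4. Scale.** Protocol 7.6 plans for a 5 mmHg difference in 24-hour SBP with SD 10 mmHg. At 80% power and two-sided 5%, this gives 63 per arm by the normal approximation and 64 by the t-test, so the plan's 64 reproduces. The standard error of a difference is 10 × √(2/64) = 1.77 mmHg. No trough SD is stated; using the same 10 mmHg is an assumption. The middle trough case is 0.15/1.77 = 0.085 standard errors and the high case is 0.50/1.77 = 0.28.

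**The case against.** The strongest objection concerns the drug mechanism. A second tablet here is the next daily dose taken slightly early, and Protocol 4.1.4 itself allows 22-26 hours between doses around visits. Protocol 1.2 gives peak levels at about 1.5 hours, so a tablet taken after 24 − 1.5 = 22.5 hours peaks after the recording ends. Protocol 1.2 also gives a terminal half-life of 12.4 hours, and Protocol 3.2 says that the effect lasts about 3 days after the last dose. Nothing in the documents shows a post-dose versus trough difference of several mmHg at steady state. This stands, and it is why the effect is rated small.

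A reader might infer that both ambulatory endpoints are compromised, or that the trial is tilted towards empagliflozin to an extent that matters. The documents do not support either. The 24-hour mean hardly moves, readings after 24 hours are already unusable, and the trough shift rests on assumed inputs. Nor does the protocol call a double-dosed recording invalid; it says only that it should be repeated.

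For Visit 2.2, Protocol 6.2.1 labels an out-of-range session unsuccessful. Under that meaning the SAP's reason would be true there. But SAP 5 fixes its own, purely technical meaning for the whole plan, so the two documents use one word in two senses.

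Finally, the SAP also cites the eCRF description, which is not available here, and parts of SAP 5 are blacked out. A dosing flag cannot be excluded. Even so, the reason as stated in SAP 6.7 would remain wrong about footnote I.

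**Conclusion.** The point holds as a minor one. A data-selection rule for two confirmatory endpoints rests on a statement about the protocol that footnote I contradicts, and that Protocol 5.1.2 and 6.2.1 contradict under the SAP's own definition of success. In those cases the plan, as far as it is visible, analyses the session that the protocol wanted replaced.

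The expected numerical effect is small. On the assumptions above, the trough bias (step III) is about 0.003 to 0.50 mmHg, at most 0.28 of a standard error, and the bias in the 24-hour mean (step II) is at most about 0.04 mmHg. If the second dose lowers SBP, the trough bias favours empagliflozin. The range also assumes that every affected session met the vendor criteria. At Visit 2.2 the issue is which baseline is analysed, with no expected difference between arms. The frequency of either situation is unknown, so the case rests on the conflict between the documents and on the low cost of removing it.

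**What to change.** Before unblinding, reconcile SAP 6.7 with footnote I and with Protocol 5.1.2 and 6.2.1:

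1. At each ABPM time point, select the first session that meets the vendor criteria and has no protocol-specified reason for a repeat. Where a repeat was done for such a reason and is successful, use the repeat.
2. Delete the statement that the protocol calls for no second session after a successful first, and say how the Visit 2.2 selection fits the general definition of baseline.
3. If no successful repeat exists, keep the first session, flag it, and add a sensitivity analysis that excludes flagged sessions. Setting the trough value to missing is not a good default. SAP 7.5.1 notes only one post-baseline ambulatory assessment up to week 12, so LOCF-H has no earlier on-treatment value to carry forward and the patient would drop out of step III.

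Affected sessions can be identified from the repeat rationale that Protocol 3.3.6 requires in source documents and from the dose and monitor times recorded under Protocol 5.1.2. The dose times named there and in Protocol 4.1.4 are those of clinic intakes, so a tablet taken at home may appear only in the rationale. A programmed check alone may therefore miss cases.

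The cost is a short SAP revision, a blinded listing of second sessions that follow a technically successful one, site queries where the reason is not in the database, and one sensitivity analysis. No new visits or measurements are needed.

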7 PLANNED ANALYSES

Disposition of the patient population participating in the trial will be analysed by study period and treatment groups and presented in the CTR as a frequency-distribution. The number of patients participating (screened, randomised, etc.) in the study will also be displayed.

A frequency of patients with iPVs, also summarised by whether the iPV led to exclusion from the PPS, will be presented by treatment group for the RS. The frequency of patients in different analysis sets will also be analysed for each treatment group.

For in-text tables presenting descriptive analysis of the endpoints and other variables (analysed in original scale), the set of summary statistics is: N (number of patients with non-missing values), mean, standard deviation (SD).

For end-of-text tables, the set of summary statistics is: N (number of patients with non-missing values) / Mean / SD / Min / lower quartile (Q1) / Median / upper quartile (Q3) / Max.

Statistical parameters will be displayed to a defined number of decimal places as specified in the BI guideline "Reporting of Clinical Trials and Project Summaries" (3).

Tabulations of frequencies for categorical data will include all possible categories and will display the number of observations in a category as well as the percentage (%) relative to the respective treatment group. Percentages will be rounded to one decimal place. The category missing will be displayed if and only if there are actually missing values. Percentages will be based on all patients in the respective patient set whether they have non-missing values or not.

In all specified statistical analyses, treatment comparisons will be made between pooled Empagliflozin (10 mg, 25 mg) and placebo.

7.1 DEMOGRAPHICS AND OTHER BASELINE CHARACTERISTICS

Descriptive analysis of the following demographic variables measured at baseline will be presented:

Sex, race, ethnicity, country, age (in years), age-groups, BMI (kg/m²), BMI categories, height (cm), smoking history, alcohol status, antidiabetic background medication categories and renal impairment (eGFR [CKD-EPI] and eCCr).

Categories for demographic and baseline characteristics are defined in [Section 6.4](#).

Descriptive analysis of the following variables measured at baseline will be presented:

HbA_{1c} (%), HbA_{1c} (mmol/mol), HbA_{1c} categories, FPG (mg/dL), FPG categories, weight (kg), weight categories, [REDACTED] SBP (mmHg), mean 24-hour SBP (ABPM) (mmHg), [REDACTED]

DBP (mmHg), mean 24-hour DBP (ABPM) (mmHg), [REDACTED]

[REDACTED] blood pressure control (SBP < 140 mmHg and DBP < 90 mmHg), [REDACTED]

Demographic and baseline characteristics will be presented for the FAS.

A summary of the number of patients in each randomisation stratum per treatment will also be shown. This will be based upon the data received from the interactive voice response system (IVRS) provider.

7.2 CONCOMITANT DISEASES AND MEDICATION

Only descriptive statistics are planned for this section of the report using the FAS.

Summaries will be presented for CTs taken during randomised treatment and those taken at baseline. Separate summaries of use of antihypertensives, ASA or lipid lowering drugs at baseline by preferred name will be presented. The displayed categories and defining anatomical-therapeutic-chemical classification (ATC) levels and ATC codes are shown in [Table 9.3: 1](#). Additionally a descriptive table of changes in dose of antihypertensive medication will be shown.

Concomitant diseases will be summarised by system organ class (SOC) and preferred term (PT). Relevant diabetic medical history by treatment group will also be presented. Both summaries will be presented using the FAS.

7.3 TREATMENT COMPLIANCE

Only descriptive statistics are planned for this section of the report.

The number and percentage of patients with overall compliance will be reported. Overall compliance will be calculated as a weighted average of reported compliance. The sum of all reported compliance over the planned visits (disregarding run-in) will be divided by the total duration (until last visit where medication is returned). The FAS will be considered.

7.4 PRIMARY ENDPOINT(S)

7.4.1 Primary efficacy analysis

A hierarchical multiple testing procedure will be used to evaluate superiority of the primary endpoint, followed by the evaluation of superiority of the key secondary endpoints in the following pre-specified hierarchical sequence:

- I. Primary endpoint: Change from baseline in HbA_{1c} (%) at week 24
- II. Key secondary endpoint: Change from baseline in mean 24-hour ambulatory SBP (mmHg) at week 12
- III. Key secondary endpoint: Change from baseline in mean trough ambulatory SBP (mmHg) at week 12
- IV. Key secondary endpoint: Change from baseline in body weight (kg) at week 24

- V. Key secondary endpoint: Change from baseline in trough seated SBP (mmHg) at week 12

Each step will be considered confirmatory if all previous steps were successful (superiority was achieved). If any of the previous steps were unsuccessful, the subsequent steps are regarded as exploratory.

The primary analysis is at 24 weeks and will be performed on the FAS (OC). It is a restricted maximum likelihood (REML)-based mixed model repeated measures (MMRM) approach comparing the change from baseline in HbA_{1c} after 24 weeks of treatment. Missing data are handled directly by the fitted model. According to published literature, MMRM analysis appears to be a superior approach for controlling Type I error rates and minimizing bias as compared to single imputation approaches such as LOCF ANCOVA analysis particularly in the presence of missing completely at random (MCAR) or missing at random (MAR) data (4).

The statistical model will be:

[figure not shown]
$$\text{HbA}_{1c} \text{ change from baseline at each on-treatment visit} = \text{overall mean} + \text{HbA}_{1c} \text{ baseline} + \text{treatment} + \text{renal function} + \text{pretreatment with metformin} + \text{visit} + \text{visit by treatment interaction} + \text{visit by HbA}_{1c} \text{ baseline interaction} + \text{random error}$$

[figure not shown]
This model includes effects accounting for the following sources of variation: ‘HbA_{1c} baseline’, ‘treatment’, ‘renal function’, ‘pretreatment with metformin’, ‘visit’, ‘visit by treatment interaction’ and ‘HbA_{1c} baseline by treatment interaction’. ‘Treatment’, ‘renal function’, ‘pretreatment with metformin’, ‘visit’ and ‘visit by treatment interaction’ are fixed classification effects, and ‘HbA_{1c} baseline’ is a linear covariate. The interaction ‘visit by HbA_{1c} baseline interaction’ will be based on the linear covariate ‘HbA_{1c} baseline’.

For each patient, the error terms from all the visits represent the within-patient variability, and are assumed to follow a multivariate normal distribution with an unstructured covariance matrix. If the model first fails to converge using an unstructured (co)variance structure, then a hierarchical approach is applied until a (co)variance structure is obtained where the model converges. Therefore the following (co)variance structures are tested according to the pre-specified order: [1] unstructured, [2] Toeplitz, [3] variance components, [4] compound symmetry. As soon as one model converges this will be the final model used, therefore no further testing of subsequent (co)variance structures is required.

The treatment effect will be estimated on the basis of the least square mean treatment difference at week 24 extracted from the primary analysis model.

[figure not shown]
The Kenward-Roger approximation will be used to estimate the denominator degrees of freedom. Significance tests will be based on least-squares means using a two-sided $\alpha = 0.05$ (two-sided 95% confidence intervals).

[figure not shown]

7.4.3 Effect of centre

Not applicable for this trial due to low patient numbers per site.

7.5 SECONDARY ENDPOINT(S)

7.5.1 Key secondary endpoint(s)

The key secondary endpoints for this study are described in [Section 5.2](#).

For the following key secondary endpoints:

- Change from baseline in mean 24-hour ambulatory SBP at week 12
- Change from baseline in trough mean ambulatory SBP at week 12

ANCOVAs will be performed based on the FAS (LOCF-H), [REDACTED]

[REDACTED] The respective model will include treatment, renal function, pretreatment with metformin, continuous baseline HbA_{1c} and continuous baseline of the respective secondary endpoint.

[figure not shown]
The results from these analyses will be presented graphically as for the descriptive values. As ambulatory measurements only provide one post-baseline assessment until week 12 (i.e. no repeated measurements), MMRM models will not be applied for these endpoints.

MMRM will be performed for the remaining key secondary endpoints (to be tested as third and fourth key secondary endpoints, respectively):

- change from baseline in body weight at week 24
- change from baseline in trough seated SBP at week 12

based on the FAS (OC) or FAS (OC-H), [REDACTED]

[REDACTED]. The model will be the same as that defined for the primary efficacy analysis with the addition of the continuous baseline key secondary endpoint as a covariate and visit by continuous baseline key secondary endpoint interaction.

Summary of hierarchical testing strategy for confirmatory analysis for superiority testing of treatment effect of Empa vs. Placebo (each step is tested at the two-sided alpha-level of 5%):

- I. Primary endpoint: Change from baseline in HbA_{1c} (%) at week 24
 - Primary analysis: MMRM on FAS (OC)
- II. Key secondary endpoint: Change from baseline in mean 24-hour ambulatory SBP (mmHg) at week 12
 - ANCOVA on FAS (LOCF-H)
- III. Key secondary endpoint: Change from baseline in mean trough ambulatory SBP (mmHg) at week 12
 - ANCOVA on FAS (LOCF-H)
- IV. Key secondary endpoint: Change from baseline in body weight (kg) at week 24
 - MMRM on FAS (OC)
- V. Key secondary endpoint: Change from baseline in trough seated SBP (mmHg) at week 12
 - MMRM on FAS (OC-H)

7.5.2 (Other) Secondary endpoint(s)

[figure not shown]
The other secondary efficacy endpoints for this study are specified in [Section 5.2.2](#).

[figure not shown]
If not specified differently for a specific endpoint, the analysis of continuous endpoints and descriptive statistics will be provided by visit for the FAS (OC) or FAS (OC-H) if applicable including actual values and change from baseline.

For the continuous exploratory endpoints (with more than one post-baseline assessment), MMRM analyses will be performed for the change from baseline at week 12 or week 24 (see Section 5.2.2) based on the FAS (OC) or FAS (OC-H) if applicable. For those endpoints with only one post-baseline assessment, an ANCOVA analysis will be performed on the FAS (LOCF) or FAS (LOCF-H) if applicable.

The respective MMRM model will include continuous baseline HbA_{1c}, continuous baseline of corresponding endpoint, treatment, renal function, pretreatment with metformin, visit by treatment interaction, visit by continuous baseline HbA_{1c} interaction and visit by continuous baseline of corresponding endpoint interaction. An unstructured covariance matrix for patient will be assumed; if this fails to converge, alternative matrices will be assessed as defined for the analysis of the primary efficacy endpoint in [Section 7.4.1](#).

ANCOVA analyses will be performed based on the FAS (LOCF) or FAS (LOCF-H) if applicable. The respective model will include treatment, renal function, pretreatment with Metformin, continuous baseline HbA_{1c} and continuous baseline of the respective endpoint.

